9.5.2. Statistical Methodology Specification (Part B)

The following pharmacokinetic statistical analyses will only be performed if sufficient data is available (i.e. if participants have well defined plasma concentration-time profiles).

Note that the intravenous PK data for bioavailability analyses will be taken from the Caucasian stratum in Part A.

Bioavailability (Part B)
Endpoint / Variables

 AUC(0-t)
Model Specification

 Analysis of variance (ANOVA) will be performed on log-transformed data to determine the point estimate for the comparison of SC and IV administration. The resulting estimated difference is the log point estimate of the absolute bioavailability (Fabs). This analysis will be conducted at the 450 mg dose level only. The 90% confidence interval for the mean difference of the log-transformed data will be calculated. The equivalent 90% confidence interval for the geometric means will be provided.
Model Checking & Diagnostics

 Normality assumptions underlying the model used for analysis will be examined by obtaining a normal probability plot of the residuals and a plot of the residuals versus the fitted values (i.e. checking the normality assumption and constant variance assumption of the model, respectively) to gain confidence that the model assumptions are reasonable. If there are any departures from the distributional assumptions, alternative models will be explored using appropriate transformed data.
Model Results Presentation

 Table of: 
 Geometric means and ratio of geometric means with 90% CI.

10. POPULATION PHARMACOKINETIC (POPPK) ANALYSES

The primary goal of this analysis is to characterize the population pharmacokinetics of GSK2831781 administered IV in Japanese and Caucasian healthy volunteers and SC in Caucasian healthy volunteers. The individual participant PK parameters will be estimated and documented for the purposes of any subsequent exposure-response (PK/PD) analyses. Any inter-ethnic differences in the PK will also be investigated.

10.1. Statistical Analyses / Methods

A summary of the planned population pharmacokinetic analyses is outlined below:

- A previous PopPK model developed based on the drug plasma and total serum sLAG3 concentrations collected during the first-time in human study 200630 (GSK Document Number 2017N352860_00) will be fitted to the drug plasma concentration-time data using the nonlinear mixed effects modelling software NONMEM.
- Individual post-hoc estimated PK parameters will be summarised descriptively.
- To support this analysis a PopPK dataset will be generated. The details for the dataset specifications are provided in [Appendix 9: Population Pharmacokinetic \(PopPK\) Analyses](#).

Detailed PopPK methodology is presented in [Appendix 9: Population Pharmacokinetic \(PopPK\) Analyses](#).

11. PHARMACODYNAMIC ANALYSES

11.1. Secondary Pharmacodynamic Analyses

11.1.1. Endpoint / Variables

Parameter	Parameter Description
LAG3+	
 • LAG3+ T cell numbers and frequencies in blood. The following cell populations will be reported: 
 ○ CD4+CD45RA-J11L1+ ○ CD4+CD45RA-REA351+ ○ CD4-CD45RA-J11L1+ ○ CD4-CD45RA-REA351+

11.1.2. Summary Measure

Absolute value and percent change from baseline (%CFB) are of interest.

Part A: Data will be available at baseline and at day 1 (6h, 24h), 4, 8, 15, 29, 43, 57, 85 and 112.

Part B: Data will be available at baseline and at day 2, 4, 8, 15, 29, 43, 57, 85 and 112.

11.1.3. Population of Interest

The secondary pharmacodynamics analyses will be based on the Safety population, unless otherwise specified.

11.1.4. Strategy for Intercurrent (Post-Randomization) Events

A ‘While on-study’ strategy will be implemented for intercurrent events.

- Withdrawn participants may be replaced in the study. Replacement participants will be dosed with the planned treatment of the withdrawn participant.
- All available data from participants who were withdrawn from the study will be listed and all available planned data will be included in summary tables and figures, unless otherwise specified.

11.1.5. Statistical Analyses / Methods

Details of the planned displays are provided in [Appendix 12: List of Data Displays](#) and will be based on GSK Data Standards and statistical principles.

Unless otherwise specified, endpoints / variables defined in Section 11.1.1 will be summarised using descriptive statistics, graphically presented (where appropriate) and listed.

11.2. Exploratory Pharmacodynamic Analyses

11.2.1. Endpoint / Variables

Parameter	Parameter Description
sLAG3	
 Concentration of soluble LAG3 in blood.
Regulatory T cells	
 CD3⁺CD4⁺CD45RA⁻CD25⁺CD127^{lo}FoxP3⁺ Regulatory T cell numbers and frequencies in blood

11.2.2. Summary Measure

Absolute value and percent change from baseline (%CFB) are of interest.

sLAG3:

Part A: Data will be available at baseline and at day 1 (1h, 2h, 6h, 12h, 24h), 3, 4, 8, 15, 22, 29, 43, 57, 71, 85 and 112.

Part B: Data will be available at baseline and at day 2, 3, 4, 6, 8, 11, 15, 18, 22, 29, 43, 57, 71, 85 and 112.

Regulatory T cells:

Part A: Data will be available at baseline and at day 4 and 112.

11.2.3. Population of Interest

The exploratory pharmacodynamics analyses will be based on the Safety population, unless otherwise specified.

11.2.4. Strategy for Intercurrent (Post-Randomization) Events

A ‘While on-study’ strategy will be implemented for intercurrent events.

- Withdrawn participants may be replaced in the study. Replacement participants will be dosed with the planned treatment of the withdrawn participant.
- All available data from participants who were withdrawn from the study will be listed and all available planned data will be included in summary tables and figures, unless otherwise specified.

11.2.5. Statistical Analyses / Methods

Details of the planned displays are provided in [Appendix 12: List of Data Displays](#) and will be based on GSK Data Standards and statistical principles.

Unless otherwise specified, endpoints / variables defined in Section 11.2.1 will be summarised using descriptive statistics, graphically presented (where appropriate) and listed.

12. PHARMACOKINETIC / PHARMACODYNAMIC ANALYSES

The primary goal of this analysis is to characterize the pharmacokinetic / pharmacodynamic (PK/PD) relationship of GSK2831781 administered IV in Japanese and Caucasian healthy volunteers and SC in Caucasian healthy volunteers. Any inter-ethnic differences in the PK/PD relationship will also be investigated.

12.1. Statistical Analyses / Methods

A summary of the planned population PK/PD analyses are outlined below:

- A previous PopPK/PD model developed based on the individual post hoc predicted PK parameters and all available cell depletion data from the first-time in human study 200630 (GSK Document Number 2017N352860_00) will be fitted to the drug plasma concentration (or PK parameters) and PD data using the nonlinear mixed effects modelling software NONMEM.
- To support this analysis a PK/PD dataset will be generated. The details for the dataset specifications are provided in [Appendix 10: Pharmacokinetic / Pharmacodynamic Analyses](#).
- Detailed PK/PD methodology is presented in [Appendix 10: Pharmacokinetic / Pharmacodynamic Analyses](#).

13. IMMUNOGENICITY ANALYSES

13.1. Endpoint / Variables

Parameter	Parameter Description
ADAs	
 Anti-drug antibodies over time.

13.2. Summary Measure

Incidence and duration of anti-drug antibodies (ADA).

The GSK2831781 immunogenicity response will be summarized for the binding antibody assay by treatment group and timepoint. The table will include the number and proportion of participants in each result category for each visit. Binding confirmatory assay results will be categorized as Negative, Positive, or Unknown. Positive samples in the binding assay are further categorized as Transient Positive (i.e. single positive response that does not occur at the final assessment) or Persistent Positive (i.e. positive response that occurs at least 2 consecutive assessments or a single result at the final assessment). Titre for samples confirming positive in the binding assay will be reported in listings.

Parts A and B: Data will be available at baseline and at day 29, 57, 85 and 112.

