| Immunogenicity | 
Non-clinical: Administration of GSK2831781 to monkeys leads to an ADA response which is more prevalent at lower doses and is associated with a reduction in GSK2831781 systemic exposure.
 
Neutralizing ADA, observed in one animal given 100 mg/kg/week SC in the 26-Week GLP study, correlated with decreased GSK2831781 plasma concentrations and were associated with immune complex mediated clinical pathology changes and increased heart rate, which were transient and of minimal magnitude.
 
Immunogenicity in nonclinical species is not predictive of the potential for immunogenicity in humans
 
Clinical: Pre-existing ADAs and post-dosing ADA have been identified in humans. No adverse reactions or alterations in PK associated with immunogenicity were observed in the FTIH study 200630.
 | 
Safety and tolerability is being assessed in participants (including clinical chemistry, haematology, AEs, hypersensitivity reactions).
 
Immunogenicity and the impact, if any, on PK and safety parameters will be monitored.
 |
| Cytokine release syndrome (CRS) | 
Non-clinical: Hyper-immune activation leading to activation of the innate immune system is only a theoretical
 | 
Appropriate monitoring for clinical symptoms associated with cytokine release such as fever, nausea, chills, hypotension, tachycardia,
 |

| Potential Risk of Clinical Significance | Summary of Data/Rationale for Risk Refer to GSK2831781 IB for details. | Mitigation Strategy |
|---|--|---|

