10.4.4. Other Analyses

For Parts A and B, the immunogenicity assessment will include the incidence (confirmed positive results only) and titres of anti-GSK2831781 binding antibodies at each time point and at any time point post baseline.

Further details of the statistical analyses will be provided in the Reporting Analysis Plan (RAP).

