2.2. Study Objectives and Endpoints

Objectives	Endpoints
Primary	

 To evaluate the safety and tolerability after single IV dosing of GSK2831781 in healthy Japanese and Caucasian participants, and SC dosing in healthy Caucasian participants 	
 AEs, vital signs, clinical laboratory values (haematology, clinical chemistry, and urinalysis), 12-lead ECG Local tolerability
Secondary	

 To evaluate the PK of GSK2831781 after a single IV dose in healthy Japanese and Caucasian participants (Part A) 	
 GSK2831781 PK parameters following single IV dose: area under the plasma concentration-time curve [AUC(0-t)], maximum observed plasma concentration (C_{max}), time of occurrence of C_{max} (t_{max})

 To evaluate the PK of GSK2831781 after a single SC dose in healthy Caucasian participants (Part B) 	
 GSK2831781 PK parameters following single SC dose: AUC(0-t), C_{max}, t_{max}, bioavailability (F)

Objectives	Endpoints

 To evaluate the effect of a single IV or SC dose of GSK2831781 on depletion of LAG3⁺ T cells in blood 	
 PK/PD relationship between plasma PK of GSK2831781 and LAG3⁺ T cells in blood over time

 To investigate the immunogenicity of single IV and SC doses of GSK2831781 	
 ADAs over time
Exploratory	

 To evaluate the concentration-time profiles of GSK2831781 after a single IV dose in healthy Japanese and Caucasian participants (Part A) 	
 GSK2831781 PK concentrations over time following single IV dose

 To evaluate the concentration-time profiles of GSK2831781 after a single SC dose in healthy Caucasian participants (Part B) 	
 GSK2831781 PK concentrations over time following single SC dose

 To evaluate the effect of a single IV or SC dose of GSK2831781 on soluble LAG3 (sLAG3) concentrations 	
 Soluble LAG3 (sLAG3) concentrations in blood over time

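### ADA incidence and the Transient/Persistent split ignore baseline antibody status, and the split leaves some post-dose patterns without a class

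*SAP*

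**What the plan says.** SAP 2.2 sets the secondary objective: "To investigate the immunogenicity of single IV and SC doses of GSK2831781". Protocol 3.3.1, in the immunogenicity row of the risk table, records that "Pre-existing ADAs and post-dosing ADA have been identified in humans". Protocol 10.4.4 says the assessment will include "incidence (confirmed positive results only) and titres of anti-GSK2831781 binding antibodies at each time point and at any time point post baseline".

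SAP 13.2 names incidence and duration as the summary measures and summarises by treatment group and time point. It says that "Binding confirmatory assay results will be categorized as Negative, Positive, or Unknown". Positives are then split in two:

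- Transient Positive: "single positive response that does not occur at the final assessment".
- Persistent Positive: "positive response that occurs at least 2 consecutive assessments or a single result at the final assessment".

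On sampling it says "Data will be available at baseline and at day 29, 57, 85 and 112". Titres go to listings only. Tables 5.4 and 5.7, and Listings 73 and 79, add no further rule. Neither document defines treatment-induced or treatment-boosted ADA.

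**The concern.** The incidence rule looks only at whether a sample taken after baseline is positive. It does not ask whether the participant was already positive before dosing, even though the protocol says such people exist. Someone whose antibody is simply unchanged by dosing enters the post-baseline count and, being positive at consecutive visits, is labelled Persistent. Elsewhere the SAP does refer to baseline: section 5.3 defines it, and sections 11.1.2 and 11.2.2 report percent change from baseline for LAG3+ cells, sLAG3 and regulatory T cells. ADA has no equivalent. Titres, the natural way to recognise a boosted response, are not used in any rule.

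The duration labels raise two further questions: whether the baseline sample counts as one of the assessments, and what to do with non-consecutive positives. At stake are the incidence and duration figures for a secondary endpoint in small groups, where one participant moves a percentage visibly.

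**Working it through.** The plan states no ADA rate, so there is no figure of its own to reproduce.

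**1. Effect of one unchanged pre-existing positive**

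Inputs (protocol 5.2): 6 active participants in each Part A ancestry stratum, and 8 in each Part B SC dose arm. SAP 13.2 summarises ADA by treatment group. Table 5.4 carries no ancestry note, whereas Tables 5.1 and 5.2 in the same list do. The Part A active IV column therefore has 6 + 6 = 12 participants.

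- Part A: 1/12 = 8.3%, against a treatment-emergent incidence of 0/12.
- Part B, either dose: 1/8 = 12.5%, against 0/8.

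**2. How likely a baseline positive is**

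The documents give no prevalence, so p is an assumption, shown from 5% to 30%. The formula is P(at least one) = 1 − (1 − p)^n.

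- n = 12, at p = 5/10/20/30%: 0.46 / 0.72 / 0.93 / 0.99.
- n = 8: 0.34 / 0.57 / 0.83 / 0.94.
- All 28 planned active participants: 0.76 / 0.95 / 0.998 / 1.00.

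These are chances of a positive baseline sample. Incidence changes only if that participant is also positive after dosing.

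**3. Is the split exhaustive?**

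Four post-dose samples (Days 29, 57, 85 and 112) give 2^4 − 1 = 15 patterns with at least one positive. Applying the SAP rules literally:

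- Transient, 3: Day 29, 57 or 85 alone.
- Persistent, 9: Day 112 alone; the three adjacent pairs; all four triples; all four visits.
- Ambiguous, 2: Days 29+112 and 57+112. Each includes the final visit, but the final result is not the only positive and the two are not consecutive.
- Neither class, 1: Days 29+85.

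Check: 3 + 9 + 2 + 1 = 15.

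**4. Does baseline count as an assessment?**

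SAP 13.2 lists baseline among the available data and does not say. For a baseline-positive participant there are 2^4 = 16 post-dose patterns, and 7 of them change class with the choice:

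- baseline only: negative becomes Transient;
- baseline+29: Transient becomes Persistent;
- baseline+57 and baseline+85: Transient becomes unclassified;
- baseline+112: Persistent becomes ambiguous;
- baseline+29+112: ambiguous becomes Persistent;
- baseline+29+85: unclassified becomes Persistent.

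**The case against.** The case for leaving the plan alone has real substance. There are no formal hypotheses, and the immunogenicity tables are final-analysis deliverables only, so they do not feed the planned interim displays. The endpoint is ADA over time, and neither document calls the incidence figure drug-induced. Baseline is a scheduled sample, so a by-visit table can show baseline positivity, placebo groups show background positivity, and Listings 73 and 79 give individual results. In the earlier study, protocol 3.3.1 reports no adverse reactions or PK changes linked to immunogenicity. A Days 29+85 participant is still counted as positive and loses only a sub-label. Reading any final-visit positive as Persistent is natural, since the Transient rule excludes the final visit. The IMM1 and IMM2 standard shells are not supplied, so their handling of baseline cannot be checked.

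Most of this limits the impact without closing the gap. By-visit counts do not show whether the same people are positive before and after dosing, and they do not correct a participant-level count "at each time point and at any time point post baseline" or the Persistent label. Placebo is too small to calibrate background: there are 4 placebo participants in each part, and at an assumed 20% prevalence the chance that none is baseline positive is 0.8^4 = 0.41. A recount from listings is possible, but it would use a classification chosen after the data are seen.

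A reader might infer a Part A effect of 1/6 (16.7%) from the stratum size. The documents do not support that, because the planned ADA summary is by treatment and not by ancestry. A reader might also infer that the plan directs pre-existing antibody to be reported as caused by the drug. No sentence says so; the effect comes from a rule with no baseline condition.

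**Conclusion.** The point holds as a defect in the summary rules for a secondary endpoint. As written, an unchanged pre-existing positive is counted in post-baseline incidence and meets Persistent Positive. Each such participant adds 8.3 percentage points to the Part A active column or 12.5 points to a Part B dose arm, assuming the planned numbers and that the antibody persists after dosing. An antibody seen only at baseline does not enter the protocol's incidence, although it could be labelled Transient if baseline counts as an assessment. How often any of this would occur is unknown.

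The classification gap is narrow: one pattern in 15 has no class and two depend on interpretation. It would be too much to say that the immunogenicity conclusions as a whole are unreliable. The analysis is descriptive, the data needed are collected, and the impact is limited to the reported incidence and duration categories.

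**What to change.** Amend SAP 13.2 before unblinding:

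- Define treatment-emergent ADA as either baseline negative with any confirmed post-baseline positive, or baseline positive with a titre rise above a multiple fixed in advance from assay validation.
- Base incidence and the Transient/Persistent split on treatment-emergent ADA, and show unchanged pre-existing ADA in its own row of Tables 5.4 and 5.7.
- State that the split uses post-baseline samples only.
- Make the split exhaustive: Persistent is positive at two or more post-baseline assessments or at the last one; Transient is every other treatment-emergent positive. Over the 15 patterns this gives 12 Persistent (11 with two or more positives, plus Day 112 alone) and 3 Transient, with none left over.
- Say how Unknown or missing results and early withdrawal are handled when identifying the last assessment.

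The cost is small: SAP wording, a derived flag, and agreement on the titre-rise multiple, which the documents do not give. Baseline samples and titres of confirmed positives are already planned, so no extra sampling is needed.

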13.3. Population of Interest

The immunogenicity analyses will be based on the Safety population, unless otherwise specified.

13.4. Strategy for Intercurrent (Post-Randomization) Events

A ‘While on-study’ strategy will be implemented for intercurrent events.

- Withdrawn participants may be replaced in the study. Replacement participants will be dosed with the planned treatment of the withdrawn participant.
- All available data from participants who were withdrawn from the study will be listed and all available planned data will be included in summary tables and figures, unless otherwise specified.

13.5. Statistical Analyses / Methods

Details of the planned displays are provided in [Appendix 12: List of Data Displays](#) and will be based on GSK Data Standards and statistical principles.

Unless otherwise specified, endpoints / variables defined in Section [13.1](#) will be summarised using descriptive statistics, graphically presented (where appropriate) and listed.

15. APPENDICES

15.1. Appendix 1: Protocol Deviation Management

Protocol deviations will be tracked by the study team throughout the conduct of the study in accordance with the Protocol Deviation Management Plan. Data will be reviewed prior to freezing the database to ensure all important deviations are captured and categorised on the protocol deviations dataset. This dataset will be the basis for the summaries and listings of protocol deviations.

15.2. Appendix 2: Schedule of Activities

15.2.1. Part A: Japanese and Caucasian Participants – IV dose

Procedure	Screening (up to 28 days before Dosing)	Day -1	Day 1 (Hours)							Days 3 – 85										Follow Up/Early Withdrawal (112 Days post dose) ³
			Pre-Dose	0 h ¹	1 h	2 h (end of infusion)	6 h	12 h	24 h	3 ₂	4 ₂	8	15	22	29	43	57	71	85	
Window			-60 min		±10 min	+30 min ⁴	±30 min	±30 min	±60 min			±1 d	±2 d	±2 d	±2 d	±3 d	±3 d	±3 d	±3 d	±7d
Informed Consent	X																			
Inclusion and Exclusion Criteria	X	X																		
Demography	X																			
Full physical examination including height and weight	X																			X
Medical history (includes substance usage)	X																			
Past and Current Medical Conditions	X																			

Procedure	Screening (up to 28 days before Dosing)	Day -1	Day 1 (Hours)							Days 3 – 85										Follow Up/Early Withdrawal (112 Days post dose) ³
			Pre-Dose	0 h ¹	1 h	2 h (end of infusion)	6 h	12 h	24 h	3 ₂	4 ₂	8	15	22	29	43	57	71	85	
Window			-60 min		±10 min	+30 min ⁴	±30 min	±30 min	±60 min			±1 d	±2 d	±2 d	±2 d	±3 d	±3 d	±3 d	±3 d	±7d
Serology (HIV, HBV, HCV, CMV, EBV, VZV)	X																			
TB screening (QuantiFERON ± PPD)	X																			
Breath Alcohol Screen	X	X																		
Urine Drug Screen	X	X																		
Haematology & Clinical Chemistry	X	X						X	X		X	X		X	X	X		X	X	
Urinalysis	X	X						X	X		X	X		X	X	X		X	X	
12-Lead ECG ⁵	X		X				X		X									X	X	
Vital Signs ⁶	X	X	X		X	X	X	X	X	X	X	X	X	X	X	X	X	X	X	X

Procedure	Screening (up to 28 days before Dosing)	Day -1	Day 1 (Hours)							Days 3 – 85										Follow Up/Early Withdrawal (112 Days post dose) ³	
			Pre-Dose	0 h ¹	1 h	2 h (end of infusion)	6 h	12 h	24 h	3 ₂	4 ₂	8	15	22	29	43	57	71	85		
Window			-60 min		±10 min	+30 min ⁴	±30 min	±30 min	±60 min			±1 d	±2 d	±2 d	±2 d	±3 d	±3 d	±3 d	±3 d	±7d	
Randomization		X																			
IMP Administration				←-----→																	
Resident in unit			←-----→																		
Local Tolerability			X			X	X	X	X												
sLAG3 concentrations			X		X	X	X	X	X	X	X	X	X	X	X	X	X	X	X	X	X
PK			X		X	X ⁷	X	X	X	X	X	X	X	X	X	X	X	X	X	X	X
Immunogenicity			X											X		X		X		X	X
LAG3 ⁺ Cell Depletion and Immunophenotyping			X				X		X		X	X	X		X	X	X		X		X
Genetic Sample ⁸			X																		
AE/ SAE Review	SAEs collected from signing of informed consent form; AEs collected continuously from time of first dose.																				
Concomitant Medication	Monitored from screening until the end of the final treatment period.																				

Procedure	Screening (up to 28 days before Dosing)	Day -1	Day 1 (Hours)							Days 3 – 85										Follow Up/Early Withdrawal (112 Days post dose) ³
			Pre-Dose	0 h ¹	1 h	2 h (end of infusion)	6 h	12 h	24 h	3 ₂	4 ₂	8	15	22	29	43	57	71	85	
Window			-60 min		±10 min	+30 min ⁴	±30 min	±30 min	±60 min			±1 d	±2 d	±2 d	±2 d	±3 d	±3 d	±3 d	±3 d	±7d
Review																				

Footnotes:

1. All post dose time points are in reference to the start of infusion.
2. Assessments at these visits should be on the scheduled day however can be at any time in the day.
3. Early withdrawal assessments will be the same as Follow-Up.
4. End of infusion assessment time window is +30 minutes for all assessments except for the PK sample which should be collected just before the end of the infusion.
5. ECG in triplicate at screening and single at all other time points.
6. Vital Signs to be taken every 30 minutes from start of infusion until completion of 2hr post dose monitoring period.
7. PK sample at end of infusion should be collected just before the end of the infusion.
8. The genetic sample is optional and can be taken any time after consent has been signed and the participant is randomized.

